2.0 Introduction

2.1 Background and Rationale

Lipedema is a connective tissue disorder that affects up to 10% of women. It is characterized by painful, swollen subcutaneous tissue and disproportionate fat accumulation (primarily in the lower limbs, however it can spread to the abdomen and arms). Patients are often not aware they are affected by this disease; rather, they think they are just overweight or obese.

Patients with lipedema often feel frustrated and uncomfortable as symptoms such as heaviness, pain, and easy bruising impact quality of life. Affected limbs can become so large and heavy that daily tasks such as walking, cleaning, or shopping become impossible.

Lipedema is a progressive disease. There are currently 3 primary stages that describe disease severity: stage 1 involves thickening of subcutaneous tissue and disproportion accumulation of subcutaneous tissue in the extremities (tissue remains smooth and is generally not heavy or swollen), stage 2 is characterized by increased fibrous tissue, leading to a nodular feel in the subcutaneous tissue which results in increased swelling and tenderness of the affected areas, stage 3 involves progression to the formation of lobules of skin and subcutaneous tissue. Symptomatic lipedema patients at stage 2 and higher almost always have secondary swelling on physical exam. This swelling results from the fat on the legs, thighs, and ankles blocking transport of lymphatic fluid; which ultimately may lead to infection. This lipo-lymphedema (or lipedema with swelling) is a secondary lymphedema, much like veno-lymphedema, and can be easily distinguished from primary lymphedema as it spares the hands and feet.

There is currently no cure for lipedema, thus treatment focuses on symptom management and improved patient-reported outcomes. At present, the two main courses of treatment include non-surgical conservative treatment (e.g., Comprehensive Decongestive Therapy (CDT), diet, exercise, emotional/psychological/social support) and lymph-sparing liposuction performed by a surgeon trained in lipedema treatment. The primary goals for treatment include: reduction/elimination of inflammation, swelling, and pain; increase in lymphatic flow, which reduces/eliminates excessive fluid and swelling; overall management of the physical impact of lipedema; and quality of life improvements

which can include emotional, psychological/mental, spiritual, and social enhancement in addition to physical management.

Intermittent Pneumatic Compression (IPC) devices are often used as home-therapy to treat secondary lymphedema or lipo-lymphedema (lipedema with swelling) and may be helpful in preventing the progression of lipedema. IPC use moves lymphatic fluid and supports the elimination of proteinaceous fluids, thus leading to improved patient-reported symptoms, decreased limb girth and volume, increased elasticity of tissues, and fewer episodes of infection (1-3). Szolnoky reported daily treatment with CDT, IPC, and multilayered short-stretch bandaging performed for 5 days led to significant improvements in leg volume, capillary fragility, and pain in women with lipedema (4).

The purpose of this study is to assess whether 3-4 weeks of IPC usage is associated with alleviation of symptoms and improvement in quality of life in women with lipo-lymphedema (lipedema with swelling).

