2.3.2 Conservative Care

Standard care for patients under the Principal Investigator's care includes 30-40 mmHg graduated compression up to waist, dietary counseling, exercise, and a referral for Complete Decongestive Therapy (CDT). Based on each patient's situation (e.g., insurance coverage, willingness/ability to independently comply with care, time constraints, etc.), some or all of these recommendations are typically followed. In this "real-world" study, no attempt is being made to control what will or won't be used in terms of conservative care since it varies in clinic practice for each patient.

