4.2 Subject Selection

The target population includes patients who have bilateral lipedema, meet the criteria listed below, and have provided informed consent.

4.2.1 Inclusion Criteria:

1. Female age 18-70 years.
2. Stage 2-3 (Schmeller Type 2-3) lipedema with secondary lymphedema.
3. Willing and able to follow prescribed care for study period.
4. Able to access (via self-pay, patient assistance, or insurance programs) prescribed care within 60 days of Baseline visit.

4.2.2 Exclusion Criteria:

1. BMI > 50.
2. Heart failure (acute pulmonary edema, decompensated acute heart failure).
3. Pacemaker or implantable cardioverter defibrillator (ICD).
4. Acute venous disease (acute thrombophlebitis, acute deep venous thrombosis, acute pulmonary embolism).
5. Severe peripheral artery disease (critical limb ischemia including ischemic rest pain, arterial wounds, or gangrene).
6. Active skin or limb infection/inflammatory disease (acute cellulitis, other uncontrolled skin or untreated inflammatory skin disease) on the arms or trunk.
7. Active cancer (cancer that is currently under treatment, but not yet in remission).
8. Poorly controlled kidney disease (glomerular filtration rate < 30 mls per minute), hypoproteinemia, pulmonary hypertension, hypothyroidism, cyclic edema, or Munchausen Syndrome.
9. Any circumstance where increased lymphatic or venous return is undesirable.

10. Currently pregnant or trying to become pregnant.

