4.4 Treatment Assignment and Duration

Eligible patients will be randomized (1:1) using sealed envelopes to one of the following treatment cohorts:

- Conservative care alone (may include 30-40 mmHg graduated compression up to waist, dietary counseling, exercise, and/or referral for CDT); or
- Flexitouch Plus with conservative care.

Following randomization, a product demo may take place to confirm the subject is able to tolerate prescribed care.

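### The eligibility criteria admit women already using a pneumatic compression pump at home, so the primary within-group change may understate the effect of IPC

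*Combined protocol and SAP*

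**What the plan says.** Section 2.1 describes home use of intermittent pneumatic compression (IPC) as common in the condition being enrolled: "Intermittent Pneumatic Compression (IPC) devices are often used as home-therapy to treat secondary lymphedema or lipo-lymphedema (lipedema with swelling". The same paragraph credits IPC with improved patient-reported symptoms and reduced limb girth. The section then gives the aim: "The purpose of this study is to assess whether 3-4 weeks of IPC usage is associated with alleviation of symptoms".

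Section 4.2 defines who may enter: "The target population includes patients who have bilateral lipedema, meet the criteria listed below, and have provided informed consent". The inclusion criteria that touch on treatment ask only for willingness ("Willing and able to follow prescribed care for study period") and for access to the prescribed care within 60 days of Baseline. The most general exclusion is "Any circumstance where increased lymphatic or venous return is undesirable". No criterion mentions a pump, past or present, and no washout is stated.

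Section 4.4 gives the control arm as "Conservative care alone (may include 30-40 mmHg graduated compression up to waist, dietary counseling, exercise, and/or referral for CDT". Section 2.3.2 says of background care that "no attempt is being made to control what will or won't be used in terms of conservative care".

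Section 6.2 collects lipedema and lymphedema history without naming IPC. Table 1 has no entry for IPC use outside the assignment. Section 13.2 makes the within-group change from Baseline the primary analysis. The between-group ANCOVA is secondary and has the Baseline value and treatment group as its independent variables.

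**The concern.** The plan itself says that pumps are common in this condition and that they improve outcomes the trial measures. A site applying Section 4.2 as written would accept a woman who already pumps every day.

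- **Device arm.** Her Baseline values already carry whatever IPC does for her. Moving to the Flexitouch Plus may add little, and her small change is averaged into the primary within-group result as if it were a response to starting IPC.
- **Control arm, pump continued.** She is on IPC at both visits, and the contrast loses her contribution.
- **Control arm, pump stopped.** Any worsening enters the control arm's change and shows up in the contrast as apparent device benefit.

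Randomisation gives the two arms the same expected share of such women. It does nothing for a within-group change, which is the primary analysis. Since pump use is not a named data item, the analyst may be unable to tell afterwards whether any of this occurred.

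**Working it through.** **1. The plan's own figure.** Section 13.1 aims at a 95% confidence interval half-width of about 0.40 SD and arrives at 15 women (30 legs) per group. With the normal quantile, n = (1.96/0.40)² = 24.01, so 25 legs. With the t quantile, 27 legs are needed (half-width 0.396 SD), which is 14 women. At 30 legs the half-width is 0.373 SD. The stated 15 is therefore reproduced to within one or two women, if the two legs of a woman count as independent. Pump use at Baseline leaves this calculation untouched. It affects what the mean change estimates, not the planned width of its interval.

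**2. Check of the criteria.** Each of the 4 inclusion and 10 exclusion criteria was read for any reference to current, recent or past pneumatic compression. None has one. The general exclusion on lymphatic or venous return does not catch these women, because for them increased return is the purpose of the pump. Section 6.5 describes permuted blocks and no stratification.

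**3. Size.** Improvement is counted as positive. All quantities below are assumptions, because the documents give none of them.

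- κ: mean change from conservative care and everything other than IPC, the same in both arms
- δ: mean change attributable to IPC in a woman not already using it
- p: share of each arm using a pump at Baseline
- g: fraction of δ that a current user still gains from the Flexitouch Plus
- s: share of current users in the control arm who stop
- w: loss when such a woman stops

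Device-arm mean change = κ + [1 − p(1 − g)]δ

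Control-arm mean change = κ − p·s·w

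Contrast = [1 − p(1 − g)]δ + p·s·w

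With g = 0 and s = 0 (current users gain nothing further and controls keep pumping), the IPC part of the device-arm change and the contrast are both (1 − p)δ:

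| p | Factor, g = 0 | Factor, g = 0.5 |
|---|---|---|
| 0 | 1.00 | 1.00 |
| 0.10 | 0.90 | 1 − 0.10 × 0.5 = 0.95 |
| 2/15 = 0.133 | 0.87 | 1 − 0.133 × 0.5 = 0.93 |
| 0.20 (3 of 15) | 0.80 | 1 − 0.20 × 0.5 = 0.90 |
| 0.30 | 0.70 | 1 − 0.30 × 0.5 = 0.85 |

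The factor applies to δ only. The device arm also receives conservative care, so its total change κ + (1 − p)δ shrinks by a smaller proportion whenever κ is positive.

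**4. Controls who stop.** Take p = 0.20, g = 0 and w = δ. If none stop, the contrast is 0.80δ. If half stop, it is 0.80δ + 0.20 × 0.5 × δ = 0.90δ. If all stop, it is 0.80δ + 0.20δ = 1.00δ. In that last case the total is restored, but a fifth of it is worsening among controls, and the control arm's own within-group change is lowered by 0.20δ. If w exceeded δ, the contrast would overshoot.

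**The case against.** The strongest reply is that the control arm is already well defined. Its name says conservative care alone, and the components listed in Sections 4.4 and 2.3.2 omit IPC. The disclaimer in Section 2.3.2 concerns only conservative care, whereas the plan treats the pump as something added to it. Section 6.5 fixes the assignment. Section 6.10 places any in-clinic Flexitouch Plus session after the Follow-up data are collected, and Section 7.2 offers controls information on the device at exit. A reader might infer that controls are free to start a pump before Follow-up. The documents do not support that: taken together, these provisions imply the opposite. What is missing is narrower. Nothing says what a woman who already owns a pump should do, or whether pump use outside the assignment counts as a deviation, and no named data item would record it.

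A second reply is that enrolled pump users may be rare. Often used is a general remark with no rate for this clinic, and IPC is not in the investigator's listed standard care. Section 6.10 has device-arm women obtain and be trained on a Flexitouch Plus, which suggests first-time users of that device. The case report forms are not in the documents, so a history form might ask about pumps. All of this stands as a reason not to assume a large p. It does not close the gap, since a new Flexitouch Plus is compatible with an older pump at home.

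A third reply is that the trial is exploratory, makes no power claim, and never says its participants are new to IPC. That is correct. A reader might infer that the change and the contrast are invalid as planned. The documents do not support that either, because with no current users there is no loss.

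**Conclusion.** The omission is certain: Section 4.2 admits current pump users, and the plan names no item that would identify them. The consequence is conditional. Under the assumptions that current users gain nothing further and that controls among them continue, the IPC-attributable part of the primary device-arm change and the between-group contrast retain a fraction 1 − p, that is 0.90 at 10% and 0.80 at 20%. Partial further benefit makes the loss smaller. Controls who stop change the make-up of the contrast and lower the control arm's own change.

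Prior use does not favour one arm in expectation, though chance imbalance is possible with 15 women per arm. The secondary ANCOVA does not repair the dilution, because the Baseline value does not identify who was pumping. This deserves correction because the remedy is cheap and protects the primary estimate. It does not show that the design fails.

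**What to change.** - **Section 4.2.2.** Add an exclusion for current or recent use of any pneumatic compression device on the legs or trunk, with a look-back period set by the sponsor. The instruments do not point to a single period: most time-referenced RAND-36 items look back 4 weeks, Pain Interference looks back 7 days, the numerical ratings refer to the present moment, and circumference has no recall period.
- **Section 6.2.** Add prior IPC use (ever, and most recent) to the lipedema and lymphedema history.
- **Follow-up, both arms.** Record any IPC use outside the assignment, with dates.
- **Section 13.2.** Analyse all women as randomised. Add a sensitivity analysis for non-assigned IPC use and label it as a post-randomisation exclusion, because it may selectively remove the most symptomatic controls.
- **Sections 4.4 and 2.3.2.** Reconcile the control arm's name with the statement that background care is not controlled, and say whether non-assigned IPC before Follow-up counts as a deviation. No treatment rule is proposed here.

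The cost is one exclusion line, one history question, one Follow-up item and a few sentences of text. The downside is that a few otherwise eligible women cannot enrol.

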4.1 Endpoint Mapping

Endpoint	Outcome Measure	Analysis
Primary	
 Circumferential Measurements 	
 Calculate percent reduction at Follow-up compared to Baseline for 6 sites on each leg as well as a composite total.
Primary	
 Quality of Life 	
 Compare Follow-up RAND SF36 score to Baseline.¹
Primary	
 Symptoms & Pain Intensity 	
 Compare Follow-up PROMIS Pain Interference², Wong-Baker Faces Scale, and the NIH Toolbox numerical rating scale (NRS) scores to Baseline.
Exploratory	
 Mobility 	
 Compare Follow-up PROMIS Mobility score to Baseline.²

¹ https://www.rand.org/health-care/surveys_tools/mos/36-item-short-form/scoring.html

² http://www.healthmeasures.net/index.php?option=com_instruments&task=Search.pagination&Itemid=992

Endpoint	Outcome Measure	Analysis
Exploratory	
 • Bioimpedance Measurements 	
 • Calculate mean reduction at Follow-up compared to Baseline for the Segmental (Right/Left Arm/Leg, Trunk) and Whole Body Extracellular Water (ECW)/Total Body Water (TBW) ratios.

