5.0 Study Assessment

Case Report Forms (CRFs) and Data Clarification Forms (DCFs) will be used for data collection and query handling. The Investigator will ensure the accuracy, completeness, and timeliness of the data recorded.

All data will be entered into an Excel spreadsheet and validated to confirm integrity of data entry. Data may be transferred to an electronic data capture system at some point. When all data have been coded, validated, and signed, the database will be locked (password protected with copy saved as PDF), and available for analysis.

The study schedule of activities is shown in Table 1.

Table 1. Schedule of Activities

Procedures	Baseline (Day 0)	Follow-up (4-12 weeks)
Informed Consent	X	
Demographics & Medical History	X	
Inclusion/Exclusion Assessment	X	
Pregnancy Test (if applicable)	X	
Vitals	X	X
Physical Exam	X	X
Circumferential Measurements	X	X [^]
Bioimpedance Measurements	X	X [^]
QOL Assessment (RAND SF-36)	X	X
Mobility Assessment (PROMIS Mobility)	X	X
Symptom & Pain Intensity Assessment (PROMIS Pain Intensity, NRS Pain & Symptom Scale, Wong-Baker Faces Scale)	X	X
Randomization	X	
Training on Flexitouch Plus and/or Conservative Care*	X	
Adverse Event, Complication, & Device Observation Assessment	X	X

* If subject is unable to obtain prescribed care and complete training on use within 60 days of the Baseline visit (e.g., due to insurance coverage/scheduling delays, etc.), the subject will be considered a screen failure.
 
[^] Optional: Circumferential and bioimpedance measurements may be taken again after an in-clinic treatment with Flexitouch Plus.
		

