6.9.1 QOL

The RAND 36-Item Health Survey (Version 1.0) taps eight health concepts: physical functioning, bodily pain, role limitations due to physical health problems, role limitations due to personal or emotional problems, emotional well-being, social functioning, energy/fatigue, and general health perceptions. It also includes a single item that provides an indication of perceived change in health. (*Appendix A*)

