6.10 Treatment

Following randomization, collection of measurements, and the completion of questionnaires, patients will be trained on the conservative care prescribed by the investigator (or designee).

Patients randomized to the Flexitouch Plus will obtain a device through standard commercial means (via self-pay, patient assistance, or insurance programs). The standard prescription of ‘Full Leg and Core (L1)’ with daily simultaneous bilateral lower extremity treatment (~60 minutes) at normal pressure levels will be used unless alternate programming is selected by the investigator. Alternate programming (e.g., twice daily, high pressure, additional supplemental lower leg program, etc.) may be used at the investigators discretion if a subject reports inadequate control of lymphedema symptoms prior to the next study visit. While alternate programming is not expected to be necessary, it is important subjects have access to the best care possible at all times in a “real world” study.

Once the prescription is submitted/processed at the Baseline visit, device shipment and training on device use must take place within 60 days or the subject will not be enrolled in the study.

At the Follow-up visit, some or all subjects may receive an in-clinic treatment with Flexitouch Plus after the Follow-up data collection is complete. Additional circumferential (including 4 sites on each leg, 1 site at the hips, and 1 site at the waist using a Gulick II tape measure) and bioimpedance (including whole body ECW/TBW ratio, as well as segmental ratios for the Right/Left Arm, Right/Left Leg, and Trunk) measurements may be collected and recorded immediately after completion of the in-clinic Flexitouch Plus treatment.

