13.2 Statistical Analysis

For continuous variables, descriptive statistics will include the number of subjects (n), mean, standard deviation, median, inter-quartile range, minimum, and maximum, based upon subjects with reported data for the variable being analyzed. Frequencies (numerator and denominator), percentages, and 95% confidence intervals will be displayed for categorical data. Percentages by categories will be based on the number of subjects with no missing (unreported) data for the specific variable being analyzed and the count of the patients for each individual level of the categorical variable (the level specific numerators). Percentages will add up to 100%, unless otherwise indicated.

There are no plans to impute missing data and there are no plans to explicitly report missing data (counts and/or percentages) in the tables for all variables as part of the planned study report content. Variations in the reported sample sizes within and/or between relevant tables can be used to ascertain insights into unreported data. In some cases, unreported data may be due to it not being clinically relevant to a particular patient or may represent expected data that was not collected. Selected analyses pertaining to unreported and/or missing data may be discussed and considered as future findings warrant.

The exploratory nature of the study suggests that the statistical focus will be on estimation and hypothesis generation and not hypothesis testing. Though p-values will be reported as apropos, point estimates, and 95% confidence intervals will be used to guide exploratory analyses for potentially clinically meaningful differences or changes to be discussed and evaluated.

Primary within treatment group analyses of change from baseline will utilize paired tests (e.g. paired t-tests, McNemar chi-square) or similar non-parametric tests as appropriate, to compare the 30-day measurement to baseline.

Secondary between treatment group comparative analyses of change from baseline will utilize ANCOVA or similar methods as appropriate. These methods will include the 30-day measurement as the dependent (response) variable, while the baseline measurement and treatment group will be the independent variables. Assessments of any interactions between the baseline measurement and treatment group will be performed.

Other exploratory comparisons, when performed, will utilize chi-square, ANOVA, t-test, and appropriate non-parametric tests, unless otherwise specified.

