13. Cut down the amount of time you spent on work or other activities	 1	 2
14. Accomplished less than you would like	 1	 2
15. Were limited in the kind of work or other activities	 1	 2
16. Had difficulty performing the work or other activities (for example, it took extra effort)	 1	 2

4/19/2019

36-Item Short Form Survey Instrument (SF-36) | RAND

During the **past 4 weeks**, have you had any of the following problems with your work or other regular daily activities **as a result of any emotional problems** (such as feeling depressed or anxious)?

- | | Yes | No |
|--|-------------------------|-------------------------|
| 17. Cut down the amount of time you spent on work or other activities |  1 |  2 |
| 18. Accomplished less than you would like |  1 |  2 |
| 19. Didn't do work or other activities as carefully as usual |  1 |  2 |

20. During the **past 4 weeks**, to what extent has your physical health or emotional problems interfered with your normal social activities with family, friends, neighbors, or groups?

- 1 - Not at all
- 2 - Slightly
- 3 - Moderately
- 4 - Quite a bit
- 5 - Extremely

21. How much **bodily** pain have you had during the **past 4 weeks**?

- 1 - None
- 2 - Very mild
- 3 - Mild
- 4 - Moderate
- 5 - Severe
- 6 - Very severe

4/19/2019

36-Item Short Form Survey Instrument (SF-36) | RAND

22. During the **past 4 weeks**, how much did **pain** interfere with your normal work (including both work outside the home and housework)?

- 1 - Not at all
- 2 - A little bit
- 3 - Moderately
- 4 - Quite a bit
- 5 - Extremely

These questions are about how you feel and how things have been with you **during the past 4 weeks**. For each question, please give the one answer that comes closest to the way you have been feeling.

How much of the time during the **past 4 weeks**...

	All of the time	Most of the time	A good bit of the time	Some of the time	A little of the time	None of the time
23. Did you feel full of pep?	 1	 2	 3	 4	 5	 6

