Appendix C. PROMIS Pain Interference

SUBJECT ID: _____

PROMIS Item Bank v1.0 – Pain Interference - Short Form 6b

DATE: _____

Pain Interference – Short Form 6b

Please respond to each item by marking one box per row.

In the past 7 days...

		Not at all	A little bit	Somewhat	Quite a bit	Very much
PAININ3	How much did pain interfere with your enjoyment of life?.....	 1	 2	 3	 4	 5
PAININ8	How much did pain interfere with your ability to concentrate?.....	 1	 2	 3	 4	 5
PAININ9	How much did pain interfere with your day to day activities?.....	 1	 2	 3	 4	 5
PAININ10	How much did pain interfere with your enjoyment of recreational activities?.....	 1	 2	 3	 4	 5
PAININ14	How much did pain interfere with doing your tasks away from home (e.g., getting groceries, running errands)?.....	 1	 2	 3	 4	 5
In the past 7 days...						
		Never	Rarely	Sometimes	Often	Always
PAININ26	How often did pain keep you from socializing with others?.....	 1	 2	 3	 4	 5

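### Six of the eight RAND-36 scales look back 4 weeks, but nothing in the plan ensures 28 days of pump use before Follow-up, so this primary endpoint can take in pre-pump days

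*Combined protocol and SAP*

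**What the plan says.** Section 2.1 states the purpose as "to assess whether 3-4 weeks of IPC usage is associated with alleviation of symptoms and improvement in quality of life". Section 4.1 lists quality of life as a primary endpoint, with the instruction "Compare Follow-up RAND SF36 score to Baseline". Section 6.9.1 says "The RAND 36-Item Health Survey (Version 1.0) taps eight health concepts", and the form is reproduced in Appendix A.

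On that form, items 13 to 32 carry a 4-week recall; the lead-in to items 23 to 31, for example, asks about "how things have been with you during the past 4 weeks". The physical functioning items ask about present limits. The general health items state no window.

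The other primary questionnaires look back less far. PROMIS Pain Interference (Appendix C) uses "In the past 7 days", the symptom rating scale (Appendix E) asks about the present moment, and the faces scale (Appendix D) asks about pain being experienced.

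Four places bear on how long the pump has been used by Follow-up:

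- Section 2.1: 3-4 weeks of use.
- Table 1 in section 5.0: "Follow-up (4-12 weeks", in a schedule whose first column is Baseline, Day 0.
- Section 13.2: the primary tests are "to compare the 30-day measurement to baseline".
- Section 6.10, with the Table 1 footnote: "device shipment and training on device use must take place within 60 days or the subject will not be enrolled in the study".

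No section links the Follow-up date to first use or sets a minimum number of days of use.

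**The concern.** A woman who has used the pump for fewer than 28 days and answers a 4-week question is describing a period that began before she had the pump. In the device arm, the answer then mixes days with and without the treatment under study. The pump's contribution to the change is understated, and so is the difference from conservative care alone. The size of this varies between women with the delivery date.

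The symptom scale and the 7-day PROMIS form are much less exposed, or not exposed at all, at the same visit. A weak RAND-36 result beside stronger symptom results could therefore be read as symptom relief without a gain in quality of life, when part of the gap comes from the recall period. The plan puts estimation ahead of testing, so the point estimates will carry the interpretation.

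**Working it through.** The documents give no figure for this overlap, so there is none to reproduce. The check has three steps.

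**1. Which items and scales are affected (Appendix A, mapped to scales by item wording).** Items with the 4-week window: 13-16 (4, role-physical), 17-19 (3, role-emotional), 20-22 (3, one social functioning and two pain), 23-31 (9, energy/fatigue and emotional well-being), 32 (1, social functioning). Sum: 4 + 3 + 3 + 9 + 1 = 20 of 36. These feed six of the eight scales. The rest are items 3-12 (10, physical functioning), 1 and 33-36 (5, general health) and 2 (1, change over a year): 10 + 5 + 1 = 16.

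**2. Share of the recall window before first use.** Let F be the Follow-up day and S the day of first pump use, both counted from Baseline. Days of use are E = F − S, and

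pre-pump share f = (28 − E)/28, held between 0 and 1.

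Reading f as attenuation needs two assumptions that are not in the documents: every recalled day counts equally, and the pump effect is full from the first day. Write the device-arm change as a conservative-care part plus a pump part P. The observed pump part is then (1 − f) × P. If conservative care contributes equally in both arms, the between-arm contrast is also (1 − f) × P.

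At the exposure stated in section 2.1:

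- 21 days: (28 − 21)/28 = 25%
- 24 days: (28 − 24)/28 = 14%
- 28 days or more: 0%

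**3. The same share under the other timings in the plan.**

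| Follow-up day F | First use S | Days of use E | Pre-pump share f |
|---|---|---|---|
| 30 | 2 | 28 | 0% |
| 30 | 7 | 23 | 5/28 = 18% |
| 30 | 14 | 16 | 12/28 = 43% |
| 30 | 30 or later | 0 | no pump exposure |
| 42 | 30 | 12 | 16/28 = 57% |
| 84 | 56 or earlier | 28 or more | 0% |
| 84 | 60 | 24 | 4/28 = 14% |

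The rows at day 30 assume that the 30 days in section 13.2 run from Baseline. The last row pairs the latest permitted start with the latest permitted visit (12 × 7 = day 84). Even waiting until the end of the window does not guarantee 28 days of use.

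**The case against.** The best defence is that the overlap may never occur. The upper end of the range in section 2.1 is 4 weeks, where f is 0. If the 30 days in section 13.2, or the 4-12 weeks in Table 1, mean time since first use, no form would cover pre-pump days. That stands as far as it goes: a reader might infer that the primary quality-of-life change is certainly diluted, and the documents do not support this. But they do not say that either period runs from first use, and Table 1 starts at Baseline. The plan allows the overlap without requiring it.

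A reader might also take 25% as the expected or largest dilution. It is neither. It applies at 21 days of use under the two assumptions above. More weight on recent days would shrink it, a gradual effect would enlarge it, and a late delivery before a day-30 visit takes the share well beyond it.

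A third tempting reading is that pre-pump days are untreated, so that each within-arm change is pulled toward zero. Section 6.10 has conservative care trained after randomization for all patients. Pre-pump days after Baseline may therefore already carry conservative-care change. What is attenuated is the pump's own contribution, and with it the between-arm contrast.

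Two further objections hold in part. First, different recall periods are properties of the instruments and are not in themselves an error; the issue is only when the RAND-36 is given. Second, the effect is small beside the sampling error. The RAND-36 has one score per woman, so with 15 women the 95% half-width is 2.145/√15 = 0.554 SD. For an assumed pump contribution of 0.5 SD, 25% attenuation is 0.125 SD. That limits the seriousness, but a bias in one direction in a primary endpoint is still worth removing when the remedy is mainly scheduling.

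**Conclusion.** The point holds in a conditional form. Six of the eight RAND-36 scales can include pre-pump days whenever use is under 28 days, and the plan does not prevent this. At the stated 3-4 weeks of use, the pre-pump share runs from 25% down to 0%. Under other readings of the schedule it ranges from nil to far above 25%. Where first use falls on or after the visit day, the problem is no longer recall but absence of exposure.

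The item count and the day arithmetic come from the documents. The step from days to attenuation rests on equal weighting of days and an immediate effect, and the scale mapping is read from item wording because the scoring page is only linked. The underlying gap is that Follow-up is not anchored to first use. The recall issue remains separable: anchoring the visit at 3 weeks of use would still leave a quarter of the window before the pump. This should be changed, but it does not undermine the trial.

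**What to change.** 1. Reconcile the durations in section 2.1, Table 1 with its footnote, section 6.10 and section 13.2, and state for each whether it runs from Baseline, from training or from first use. Which duration of use is intended is for the sponsor and investigator to settle.
2. In Table 1 and section 6.9.1, schedule the Follow-up RAND-36 for when at least 28 days have passed since first home use. This is a condition on when the form is given, set by its recall period. Time control-arm visits so that days from Baseline stay comparable between arms; otherwise the device arm would have had longer conservative care at assessment, which could confound the ANCOVA comparison.
3. Record the date of first home use on the case report form.
4. In section 13.2, flag the six 4-week scales on any form completed before 28 days of use, and add a sensitivity analysis without them. Report physical functioning and general health as usual.

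With a gradual effect, a 4-week average still lags the woman's current state after 28 days. The rule removes pre-pump days from the window but does not make the scales a snapshot, and the report should say so.

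Cost: protocol wording, one date field and one additional analysis, with no new visit or instrument. Some visits move later. A day-60 start needs day 60 + 28 = 88, four days past the 12-week limit, so the window must be extended slightly. In the extreme, a visit that would have been on day 28 moves by 60 days.
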